11. EFFICACY AND EXPLORATORY ANALYSES

All efficacy and exploratory analyses will be conducted for ITT and PPS. Listings for all efficacy and exploratory endpoints will be provided at each scheduled timepoints for the ITT population, with an additional flag indicating the inclusion in PPS. All of these will be provided for each treatment arm, sorted by patient ID, along with the age, sex and baseline weight of the patient.

11.1 Primary Efficacy Analysis

For patients who died, their WHO7 responses of 7 (death) will be carried forward to all applicable visits. For example, a patient who died on Day 9, will be recorded as having WHO7 response of 7 on Day 11, 15 and 29.

The SOC and treatment arms under WHO7 ordinal scale will be compared with respect to the primary endpoint using proportional odds models (ordinal logistic regression) adjusted for site and age. Treatment will be compared to SOC by testing whether the common odds ratio differs from 1.0 at day 15 using two-sided tests at 2.5% level of significance under the ITT population set, followed by PP population set. All modeling assumptions will be verified.

The relevant SAS code for proportional odds model takes the following form, where Treatment represents SOC, Arm A, Arm B and Response represents the WHO7 ordinal scale categories.

```
proc logistic data=dataset;  
class Treatment Response Site/ param=ref ref=first;  
model Response = Treatment Age Site;  
run;
```

The odds ratio under the fitted proportional odds model will be reported for Arm A and B vs SOC, along with the Wald 95% CI and corresponding Chi-squared p-value. Score test p-value testing the assumption of proportional odds will also be reported. To adjust for multiple comparison, p-values must be < 0.025 to be considered statistically significant. P-values < 0.05 may still be considered as potentially promising for the next study phase.

In addition, counts and percentages of patients in each of the WHO-7 category will also be reported for each treatment arm.

Separate 95% CIs (Newcombe) and p-values (Chi-Squared test without continuity correction) will be computed across each of the ordinal scale between SOC and treatment arms A and B. To adjust for multiple comparison, p-values must be $< \frac{1}{280}$ or (0.05/14) to be considered statistically significant. The reason for adopting the most stringent rule for multiple adjustment is because this pilot phase of the study is essentially exploratory in nature, and care must be taken to minimize the event of a premature conclusion being made purely due to chance.

The above analyses will be done for ITT and PPS.

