### 5.1 Inclusion Criteria

1. Male and female subjects aged  $\geq 18$  years of age
2. Confirmed coronavirus infection
  - a) Positive real-time fluorescence polymerase chain reaction of the patient's respiratory or blood specimens for SARS-CoV-2 nucleic acid
  - b) Viral gene sequences in respiratory or blood specimens that are highly homologous to SARS-CoV-2
  - c) Any other diagnostic test accepted by local regulatory authorities
3. Must be hospitalized and requiring supplemental oxygen, or on non-invasive ventilation or high flow oxygen devices (Score of 4 or 5 on WHO Ordinal Clinical Scale)
4. Female subjects of childbearing potential who are sexually active with a non-sterilized male partner must use at least 1 highly effective method of contraception (e.g. oral contraceptives, intrauterine device, diaphragm plus spermicide) from the time of screening and must agree to continue using such precautions for 90 days after the final dose of study drug(s)

5. Non-sterilized males who are sexually active with a female partner of childbearing potential must use condom plus spermicide from day 1 through 90 days after receipt of the last dose of study drug(s)
6. Subjects (or legal designate) must have the capacity to understand, sign and date a written, informed consent form and any required authorization prior to initiation of any study procedures

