## 7.3 Visits

### 7.3.1 Visit 1 (Screening/Baseline/Enrollment)

At Visit 1, information will be collected for evaluation of trial eligibility by provided information as follows and patients will be randomized and dosed after confirmation of eligibility:

- Signing ICF (prior to any trial-related activities)
- Inclusion criteria and exclusion criteria
- Demographics (gender, date of birth, race and ethnic origin) and relevant medical and surgical history
- Confirmation of COVID-19 diagnosis (SARS-CoV-2 RNA confirmation). Include dates of onset of symptoms (if available) and initiation of treatment.
- Pregnancy test (females of reproductive age; Romania: Serum beta-human chorionic gonadotropin [ $\beta$ -HCG]; Rest of World: Serum beta-human chorionic gonadotropin [ $\beta$ -HCG] or urine test is acceptable)
- Vital signs measurements (including pulse, respiration rate, body temperature, systolic and diastolic blood pressure measured with the patient in a seated position [if possible] after  $\geq 3$  minutes of rest), and SpO2. Body weight and height will be included for the screening visit only
- Limited Physical Exam
- Assess baseline measures of clinical support
  - Hospitalized
  - Oxygen requirement
  - Non-invasive mechanical ventilation (via mask)
  - Mechanical ventilator requirement (via endotracheal tube or tracheostomy tube)
  - ECMO requirement
  - Ordinal Scale Assessment
    1. Not hospitalized, no limitations on activities
    2. Not hospitalized, limitation on activities
    3. Hospitalized, not requiring supplemental oxygen
    4. Hospitalized, requiring supplemental oxygen
    5. Hospitalized, on non-invasive ventilation or high flow oxygen devices
    6. Hospitalized, on invasive mechanical ventilation or ECMO
    7. Death
  - For the purposes of eligibility/baseline the worse score from the previous day (Day -1) will be used
  - NEW Score
- Safety laboratory testing
- Child-Pugh Score
- Cytokine Markers
- PaO2 and PaO2/FiO2 ratio
- ECG
- VAS (if possible)
- Extent of Dyspnea (if possible). For the first questionnaire (at baseline), the patient compares their current shortness of breath to their shortness of breath when they are well.)
- Concomitant medications documented
- Randomization\* after eligibility confirmation. All screening/baseline procedures must be completed prior to randomization and administration of study medication.

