2.6 Randomization

Static randomization using block size of 3 will be employed with stratification by site and age (<65 versus ≥65). Patients who withdraw from the study or are lost to follow-up after signing the informed consent form and randomization will not be replaced.

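### The Phase 2b primary proportional odds model leaves out the WHO-7 entry score (4 or 5); adding it would guard cheaply against chance severity imbalance, and baseline WHO-7 needs a one-line clarification.

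*SAP*

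**What the plan says.** - **Primary model.** SAP 11.1 analyses Day 15 WHO-7 status "using proportional odds models (ordinal logistic regression) adjusted for site and age", and its SAS code agrees: "model Response = Treatment Age Site". Protocol 10.9.1 and the synopsis name the same two covariates.
- **Entry and randomization.** Protocol 5.1 requires a "Score of 4 or 5 on WHO Ordinal Clinical Scale". SAP 2.6 randomizes in blocks of 3 "with stratification by site and age", so the entry score is not a stratum.
- **The score is available in time.** Protocol 7.3.1 says: "For the purposes of eligibility/baseline the worse score from the previous day (Day -1) will be used". It adds: "All screening/baseline procedures must be completed prior to randomization and administration of study medication".
- **Where severity does appear.** The secondary WHO-7 mixed model (SAP 11.4.2) has a baseline term but treats the scale as continuous. Protocol 4.1 and SAP 2.1 plan to examine versions of the scale by severity. Neither adjusts the primary odds ratio. The NEWS change-from-baseline model (SAP 11.5.2) lists no baseline term.
- **How the result is used.** SAP 11.1 sets p < 0.025 for significance and adds: "P-values < 0.05 may still be considered as potentially promising for the next study phase". It also says that "this pilot phase of the study is essentially exploratory in nature".
- **General baseline rules.** Protocol 10.4.1 takes the latest value before first study drug. SAP 3.2 takes the Day 1 value, falling back to the last value before first study treatment.

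**The concern.** With about 50 patients per arm, the share entering at score 5 can differ noticeably between arms by chance. Neither the randomization nor the primary model accounts for this. If entry score predicts Day 15 status, the estimated odds ratio absorbs part of the difference. A gap in the drug's favour can make an inactive dose look promising, and a gap against it can hide a real effect. Protocol 4.1 links Phase 3 numbers to the Phase 2b outcome, so the estimate will be used even though the stage is exploratory.

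The covariate also needs one unambiguous baseline. Under the daily rule in Protocol 7.3.2 and 7.4.4, the score labelled Day 1 is the worst status of Day 1, recorded on Day 2. Protocol 6.2 puts the first dose on Day 1, so that score can cover time after dosing. It must not be confused with the eligibility score.

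**Working it through.** **1. The plan's own figure.** Only the pivotal stage is powered. Whitehead's formula for 1:1 allocation is N = 12(z₀.₉₇₅ + z₀.₉₀)² / [(log OR)²(1 − Σp̄³)], where p̄ averages the two columns of Table 2 (the treatment column sums to 99.88% and is rescaled to 100%).
- Σp̄³ = 0.1266, so N = 12 × (1.960 + 1.282)² / (0.5596² × 0.8734) = 461.0. That is 231 per arm, 462 in total.
- 462/0.9 gives 514 enrolled.

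Both figures reproduce and are not in question. The same formula at 50 per arm gives 23% power for OR 1.75 at two-sided 2.5%; the plan claims no power for Phase 2b.

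**2. Assumptions not in the documents.** Share at score 5: 30–50%. Odds ratio of score 5 versus 4 for a worse Day 15 status: 2–5.

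**3. How often the arms differ.** Exact binomial, two independent arms, gap of at least 10 points:

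| Per arm | Either direction | Favouring a given dose | Favouring at least one of two doses |
|---|---|---|---|
| 50 (gap ≥ 5 patients) | 33–37% | 16–18% | 26–29% |
| 56 = 168/3 (gap ≥ 6 patients) | 26–30% | 13–15% | 21–24% |

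At a 20% share, the either-direction figures fall to 26% and 19%.

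**4. How far a gap moves the estimate.** The shift in log OR is roughly the gap times the log prognostic OR. For a 10-point gap:
- OR 2: 0.10 × 0.693 = 0.07
- OR 3: 0.10 × 1.099 = 0.11
- OR 5: 0.10 × 1.609 = 0.16

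Against a standard error of 0.38, these are 0.18, 0.29 and 0.42 standard errors, equivalent to a null OR of 1.07, 1.12 or 1.17.

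Simulation confirms this. It used 150 patients allocated 1:1:1 over 10 sites in blocks of 3 within site and age, the SOC column of Table 2, and assumed an age OR of 1.3 per 10 years, a site SD of 0.3 and a between-site SD of 0.5 for the score-5 logit. Both models included age and site. The shifts were 0.07–0.08, 0.11–0.12 and 0.15–0.17; with the score added they were under 0.01.

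**5. Chance of p < 0.05 in the drug's favour, one dose versus SOC (same simulation).**

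| True effect | Gap of at least 10 points | Site and age only | With entry score |
|---|---|---|---|
| None | Favourable | 5.3–8.7% | 2.9–3.3% |
| None | Unfavourable | 0.2–1.5% | 2.6–3.0% |
| None | All trials | 2.9–3.2% | 3.0–3.1% |
| OR 1.75 | Favourable | 43–51% | 32–33% |
| OR 1.75 | Unfavourable | 12–24% | 33–35% |
| OR 1.75 | All trials | 28–34% | 32–34% |

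Over all trials, the two models fall on different sides of p < 0.05 in 1.1–2.2% of null comparisons and 5–12% of comparisons with OR 1.75.

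**6. Average properties at two-sided 2.5%.** Type I error is 3.0–3.3% for both models with 10 site terms and 2.4% for both without them, so the small excess comes from the site terms and not from the missing score. Power for OR 1.75 is 19–24% without and 23–25% with the score. A separate simulation without site and age found 21–22% versus 21–23% at prognostic OR 2, and 19–20% versus 22–23% at OR 4.

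**7. The baseline rules side by side.** Only Protocol 7.3.1 and 7.4.4 are written for WHO-7. They use the worse Day −1 score, gathered at Visit 1. That is also the latest value collected before dosing (Protocol 10.4.1) and, because the schedule labels Visit 1 as Day 1, plausibly the Day 1 value of SAP 3.2. Two loose ends remain. A different score will later carry the Day 1 label. And the general rules are anchored to first study drug or study treatment, while SOC-only patients receive no ifenprodil and no other anchor is named.

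**The case against.** The strongest reply is that the plan adjusts for exactly its stratification factors, which is a defensible choice. Type I error is the same either way, the average power gain is small, and no Phase 2b power is promised. Imbalance would be visible, because SAP 11.4.2 tabulates WHO-7 at baseline by arm and its treatment-by-day contrasts give baseline-adjusted Day 15 comparisons. The severity review also brings entry status into Phase 3 planning. The striking rows in step 5 condition on a minority event (13–16% for a favourable gap in the simulation) and rest on assumed inputs.

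Most of this stands and limits the point. It does not remove it: SAP 11.4.2 analyses the scale as continuous, and the severity review compares versions of the scale, so neither corrects the odds ratio that the plan reports as primary.

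A reader might also infer that the documents contain three competing WHO-7 baselines, or that the SAP deliberately uses a post-dose one. They do not support that. SAP 3.2 admits repeat or unscheduled values only when the baseline visit value is missing, which points to Visit 1 rather than to a daily score collected on Day 2. The general rules are probably meant to give the pre-dose Visit 1 value. What is needed is a clarification.

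**Conclusion.** The primary model should include the entry score. The omission is certain from the text. Its size is moderately certain, because the score-5 share and the prognostic OR are assumptions. The average benefit is about 1–4 power points for a prognostic OR of 2–5 and negligible at OR 2 or less. The main benefit is conditional: protection in either direction against a shift of 0.2–0.4 standard errors, arising from a gap that occurs in 33–37% of comparisons at 50 per arm (26–30% at 56).

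Three stronger readings are not supported. The omission does not invalidate or inflate the randomized test (step 6). It does not affect the stated 462 or 514 patients. And it does not feed a binding go/no-go rule: SAP 11.1 says only that p < 0.05 may be considered promising, and describes the stage as exploratory. Adjustment will not cure the low Phase 2b power either.

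**What to change.** 1. **Primary model.** In SAP 11.1, add baseline WHO-7, coded ≤4 versus ≥5, to the text, the class statement and the model statement (Treatment, Base_WHO7, Age, Site). The two-level coding stops an ineligible patient kept in the ITT set from creating a sparse level. Amend Protocol 10.9.1 and the synopsis to match. Keep the site-and-age model as a sensitivity analysis, and label the new odds ratio as conditional on baseline score.
2. **Clarification.** State that baseline WHO-7 for SAP 11.1 and 11.4 is the eligibility score recorded at Visit 1 before randomization, not the daily score later labelled Day 1. Anchor it to randomization, which exists in all three arms.
3. **Separate minor item.** Add baseline NEWS to the SAP 11.5.2 model.

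**Cost.** No new data are needed. The change requires a SAP revision and a protocol amendment (Protocol 11.1), with ethics committee approval if it is judged substantial. The estimand becomes a conditional odds ratio, and the model standard error rises slightly (0.38 to 0.38–0.39 under no effect). Because the stage is open label and the 75-patient interim presents Day 15 WHO-7 results, the change must be dated before by-arm Day 15 data are reviewed. If that is no longer possible, the adjusted model should be labelled a sensitivity analysis.

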**NUMBER OF SUBJECTS FOR THE PIVOTAL PHASE 3 STAGE OF THE STUDY:**

For the pivotal phase, a sample of 462 patients (231 in the SOC group and 231 in the active treatment group/s) achieves 90% power to detect a change in the log odds ratio of 0.5596 when the significance level (alpha) is 0.05 using a two-sided test. A log odds ratio of 0.5596 corresponds to an odds ratio of 1.75 comparing treatment to SOC. To account for drop out of 10%, a total of 514 patients will be enrolled.

**Phase 2b Interim analysis and increasing the patient number:** An interim analysis will be conducted on the ITT population when 75 patients complete the clinical status assessment at day 15 (the primary endpoint). A preliminary full analysis report of 150 patients with up to Day 29 entered will also be presented. An interim analysis that allows stopping for futility or efficacy will be considered for Phase 3. Details for the Phase 3 futility or efficacy analysis will be specified in the Phase 3 Statistical Analysis Plan and DSMB Charter as appropriate.

**PRIMARY EFFICACY PARAMETER:** Patient clinical status (on the [WHO 7-point ordinal scale](#)) at day 15 in IP versus SOC control group patients:

1. Not hospitalized, no limitations on activities
2. Not hospitalized, limitation on activities
3. Hospitalized, not requiring supplemental oxygen
4. Hospitalized, requiring supplemental oxygen
5. Hospitalized, on non-invasive ventilation or high flow oxygen devices
6. Hospitalized, on invasive mechanical ventilation or ECMO
7. Death

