### 10.3 Sample Size and Power Considerations

For the pilot Phase 2b phase, a sample of 150 patients (50 in Arm A, Arm B and SOC) will be recruited. To account for drop out of 10%, a total of 168 patients will be enrolled.

For the pivotal Phase 3 phase, A sample of 462 patients (231 in the SOC group and 231 in the active treatment group) achieves 90% power to detect a change in the log odds ratio of 0.5596 when the significance level (alpha) is 0.05 using a two-sided test. A log odds ratio of 0.5596 corresponds to an odds ratio of 1.75 comparing treatment to SOC. The sample size was estimated using the *Tests for Two Ordered Categorical Variables* module in [PASS 14](#). To account for drop out of 10%, a total of 514 patients will be enrolled.

The sample size assumes that the distribution of patients on day 15 will be as shown in [Table 2](#), which is scenario 4 in the WHO master protocol (2020) for enrolled patients with moderate to severe disease under an odds ratio of 1.75.

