### **10.9 Efficacy**

#### **10.9.1 Primary Efficacy Analysis**

The SOC and treatment arms under WHO7 ordinal scale will be compared with respect to the primary endpoint using proportional odds models (ordinal logistic regression) adjusted for site and age. Treatment will be compared to SOC by testing whether the common odds ratio differs from 1.0 at day 15 using two-sided tests at 2.5% level of significance under the ITT population set, followed by PP population set. All modeling assumptions will be verified.

Separate 95% CI and p-values will be computed across each of the ordinal scale between SOC and treatment arms for both ITT and PP population sets. Multiple comparison techniques (to be detailed in the SAP) will be employed to ensure type I error is controlled to 5% for these comparisons.

If, following the Phase 2b interim analysis or final analysis, the primary endpoint changes for Phase 3, details will be written in the SAP, and a protocol amendment will be created.

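### Do the 95% interval beside the p < 0.025 rule, and the unlabelled 2.5% test beside Phase 3 power at 5%, make the primary analysis inconsistent?

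*SAP*

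**What the plan says.** **Phase 2b.** The SAP limits itself to Phase 2b (section 1). Its section 11.1 compares each of the two doses with standard of care (SOC) by a proportional odds model adjusted for site and age. The odds ratios "will be reported for Arm A and B vs SOC, along with the Wald 95% CI and corresponding Chi-squared p-value". The rule for significance follows in the same paragraph: "To adjust for multiple comparison, p-values must be < 0.025 to be considered statistically significant". A second, weaker tier comes next: "P-values < 0.05 may still be considered as potentially promising for the next study phase".

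**Protocol test.** Section 10.9.1 states that "The SOC and treatment arms under WHO7 ordinal scale will be compared with respect to the primary endpoint", by "testing whether the common odds ratio differs from 1.0 at day 15 using two-sided tests at 2.5% level of significance". The synopsis gives the same level. Neither place names a phase. Section 10.9.1 then looks ahead to the case in which "the primary endpoint changes for Phase 3, details will be written in the SAP".

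**Phase 3 power.** Protocol 10.3 says that 231 patients per group "achieves 90% power to detect a change in the log odds ratio of 0.5596 when the significance level (alpha) is 0.05", two-sided. The synopsis and SAP 2.5 give the same figures.

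**What is left open.** Protocol 4.1 makes the Phase 3 number depend on the Phase 2b outcome, adds a placebo arm and leaves the details to an amendment. Protocol 4.2 and 10.3 also allow the size and several design features to change. The synopsis refers to a separate Phase 3 SAP.

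**The concern.** There are two apparent mismatches.

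The first is between interval and rule. A Wald 95% interval excludes 1 exactly when the Wald p-value is below 0.05. For p between 0.025 and 0.05, the table would show an interval clear of 1 beside a result that the plan calls not significant. No 97.5% interval is specified, and no note says that the 95% interval is unadjusted. Someone who reads only the interval could credit a dose with an effect that the plan does not, and these results feed the planning of Phase 3.

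The second is between the primary test and the Phase 3 sample size. The only primary test the protocol states is at two-sided 2.5%, in a document that covers both phases, while the Phase 3 size rests on two-sided 5%. If the 2.5% test governed Phase 3, the stated 90% power would be too high.

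**Working it through.** **Inputs.** Odds ratio 1.75, so ln 1.75 = 0.5596 (protocol 10.3). Day-15 distribution from protocol Table 2, categories 7 to 1: SOC 2, 1, 2, 5, 17, 36, 37%; treatment 1.0, 0.6, 1.2, 3.03, 11.45, 31.90, 50.70%. Phase 2b has about 50 patients per arm (protocol 4.1). Normal quantiles: 1.960 (two-sided 0.05), 2.241 (two-sided 0.025), 1.282 (90% power). The calculation does not adjust for site and age, which is an assumption.

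**1. Reproduce the Phase 3 size.** The Whitehead formula for equal groups is

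N = 12 (z_α + z_power)² / [(ln OR)² (1 − Σp̄³)],

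where p̄ is the mean of the two Table 2 columns in each category: 0.015, 0.008, 0.016, 0.04015, 0.14225, 0.3395, 0.4385. Then Σp̄³ = 0.1264 and 1 − Σp̄³ = 0.8736.

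At two-sided 0.05: N = 12 × (1.960 + 1.282)² / (0.3132 × 0.8736) = 460.9, or 462 as an even number of whole patients. This is the stated figure, and 462 / 0.9 gives 514 after rounding up. The sample size therefore rests on 5%.

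**2. Phase 3 power at each level.** With N = 462, the information is V = (462 / 12) × 0.8736 = 33.63 and √V = 5.80, so ln OR × √V = 3.245.

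- At 0.05: Φ(3.245 − 1.960) = 90.1%.
- At 0.025: Φ(3.245 − 2.241) = 84.2%. Keeping 90% power would take 544.4, or 546 patients.

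**3. Phase 2b: where the interval and the rule part.** With 100 patients per comparison, V = (100 / 12) × 0.8736 = 7.28, so SE(log OR) = 1 / √7.28 = 0.371.

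- Smallest observed odds ratio with p = 0.05: exp(1.960 × 0.3706) = 2.07.
- Smallest with p = 0.025: exp(2.241 × 0.3706) = 2.29.
- Example inside the zone, p = 0.03: odds ratio 2.24, 95% CI 1.08 to 4.62, 97.5% CI 0.97 to 5.13.

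**4. How often it happens.** At a true odds ratio of 1.75, ln OR / SE = 1.510.

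- Chance that p < 0.05: Φ(1.510 − 1.960) = 32.6%.
- Chance that p < 0.025: Φ(1.510 − 2.241) = 23.2%.
- Difference: 9.4 percentage points per dose, which is 9.4 / 32.6 = 29% of the occasions on which the 95% interval excludes 1.

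These figures borrow the Phase 3 planning distribution and effect; neither document states an effect or a power target for Phase 2b. With no effect the share is half, simply because 0.025 is half of 0.05.

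**5. Does the mismatch touch the error rate?** No. The verdict uses p < 0.025 for each dose. Two comparisons at 0.025 give at most 2 × 0.025 = 0.05, and about 4.6% with the correlation of 0.5 that a shared, equal-sized control induces. The interval plays no part in the rule.

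**6. Which phase does 2.5% belong to?** SAP 11.1 repeats the protocol's 2.5% sentence, in a document confined to Phase 2b, and gives multiple comparison as the reason for the 0.025 threshold. Phase 2b has two dose comparisons, and 0.05 / 2 = 0.025. The power statement in protocol 10.3 concerns one active group of 231 against a control group of 231, where 5% needs no such division. The two levels answer different questions.

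**The case for a change.** The strongest case for a change is that the zone is not a rarity. Under the planning effect, almost three in ten of the 95% intervals that exclude 1 would accompany a result called not significant. SAP 11.1 itself, on the category-by-category comparisons, stresses avoiding premature conclusions due to chance. Adding a 97.5% interval costs four lines of output (two doses, two populations), each interval 2.241 / 1.960 = 1.14 times as wide on the log scale. On the second point, the synopsis allows for more than one Phase 3 active group, so the reading that places 2.5% in Phase 2b alone is an inference.

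What stands is that a reader would be helped by a note that the 95% intervals are nominal, and that the 2.5% level lacks a phase label. What does not stand is that either omission alters a result. The p-value sits beside the interval and the threshold is explicit. The 95% interval is a valid nominal interval, and it matches the p < 0.05 tier that the SAP sets for interest in the next phase. Nominal 95% intervals are also the reporting convention of both documents: SAP 11.1 prints them for the category comparisons judged at 0.05 / 14 = 0.0036, where a matching interval would be at about 99.64%. A second interval for the odds ratios alone would leave that larger gap as it is. The number of Phase 3 active arms is open, but it is expressly left to the amendment, where the Phase 3 level and size must be settled in any case.

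**Conclusion.** No change follows. Applied as written, SAP 11.1 gives one verdict per dose, based on the printed p-value, with the type I error over the two doses held within 5%. A matched 97.5% interval would change no test, estimate or decision; it is a matter of presentation. The discrepancy is confined to p between 0.025 and 0.05, or observed odds ratios of about 2.07 to 2.29 at 50 per arm, on the assumption of Table 2 rates and no covariate adjustment.

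The missing phase label is a gap that the rest of the documents fill. Read together, they place 2.5% with the two Phase 2b dose comparisons and 5% with a single Phase 3 comparison. On that reading the stated 462 patients and 90% power are right (90.1% on recalculation). The 84.2% would apply only if 2.5% were carried into Phase 3, and nothing in either document says that it is. The Phase 3 figures are provisional and await the planned amendment.

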2. PROJECT OVERVIEW

2.1 Study Design

This is a Phase 2b/3, multicenter, open label, randomized, parallel group study to evaluate the efficacy of Ifenprodil in patients with coronavirus disease of 2019 (COVID-19) disease.

In the Phase 2b phase, patients will be randomized in a ratio of 1:1:1 to either a) 20 mg TID IP plus Standard of Care group, b) 40 mg TID IP plus Standard of Care or c) Standard of Care only group. Investigators will collectively enroll approximately 50 evaluable patients in each treatment group, for a total of 150 patients. Patients receive either oral Ifenprodil (20 or 40 mg ter in die (TID)) for up to 14 days in addition to Standard of Care, or Standard of Care only. The Standard of Care (SOC) for each patient will be captured in the electronic clinical reporting form (eCRF).

Randomization will be stratified by site, and age (<65 versus ≥65).

For Phase 2b, one interim statistical analysis will be performed on selected efficacy endpoints and for safety for each arm after the first 75 patients have completed up to 2 weeks of treatment (Day 15). This analysis is being done to allow safety assessment and some snapshots of efficacy assessments as the trial progresses.

The Phase 2b study will also evaluate the different constructs of the ordinal scale (different days and different number of categories) by severity (severe vs. mild-moderate). Data from the Phase 2b study will be used to down select and prioritize the secondary endpoints. The protocol would then be amended for Phase 3 study to include the additional required number of patients to be recruited for the study to meet statistical significance in its primary endpoint.

An additional placebo arm will be added in the Phase 3 portion of the study. The number of participants to be enrolled in Phase 3 pivotal stage will be determined based upon the outcome of pilot Phase 2b stage of the study. Participants will be randomized to receive investigational product (IP) plus SOC, or Placebo plus SOC. Details will be outlined in a protocol amendment

Figure 1: Trial Design

[figure not shown]

Table 1 Schedule of Events

Trial Activity	Screening/Baseline/ Enrolment visit	Daily until hospital discharge	End of treatment	Follow-up period	
Day	1	2-14	15	29	60
Allowed window for visit (±)	-1 ^a		2	2	3
Visit	1		2 ^b	3	4
Informed consent	•				
Inclusion/exclusion criteria including confirmation of COVID-19 diagnosis	•				
Confirmation SARS-CoV- 2 ^h	•	•	•	•	
Pregnancy test	•				

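### The fixed 0.025 level per dose is valid, but Holm's procedure keeps the same 5% family-wise bound and can add a second dose

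*SAP*

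**What the plan says.** SAP 2.1 describes three arms: "patients will be randomized in a ratio of 1:1:1" to 20 mg TID plus SOC, 40 mg TID plus SOC, or SOC alone. SAP 2.5 plans 50 per arm, with 168 enrolled to allow for dropout, and states no effect size or power for this stage.

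The primary analysis in SAP 11.1 is a proportional odds model with "two-sided tests at 2.5% level of significance under the ITT population set, followed by PP population set". Two comparisons come out of it: "The odds ratio under the fitted proportional odds model will be reported for Arm A and B vs SOC". The level is then given as a multiplicity rule, "To adjust for multiple comparison, p-values must be < 0.025 to be considered statistically significant", and the next sentence adds: "P-values < 0.05 may still be considered as potentially promising for the next study phase". Protocol 10.9.1 and the synopsis give the same 2.5% level. Neither document mentions a step-down procedure.

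A separate rule covers the category-by-category tests: p must be below 1/280, "or (0.05/14) to be considered statistically significant". A justification follows that rule: "The reason for adopting the most stringent rule for multiple adjustment is because this pilot phase of the study is essentially exploratory in nature". The protocol's explicit 5% target, that multiple comparison techniques "will be employed to ensure type I error is controlled to 5% for these comparisons", is also attached to the category-wise tests. For the two doses, a 5% family-wise target is implied by 0.05/2 and not stated.

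**The concern.** With two hypotheses, a fixed 0.025 for each spends no more than 5% in total, but it does not reuse the 0.025 that is freed once one dose has been declared significant. Holm's procedure does. It compares the smaller p-value with 0.025 and, only if that passes, the larger with 0.05. It holds the 5% bound under any dependence between the tests, so the shared SOC arm is no obstacle.

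The two rules differ in one situation: one dose has p < 0.025 and the other has p between 0.025 and 0.05. Bonferroni then declares one dose significant and Holm declares both. Phase 2b informs the design of Phase 3, and the synopsis leaves open whether Phase 3 has one or more active groups. A formal answer on the second dose is therefore of some use.

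**Working it through.** **The plan's own figures.** 0.05/2 = 0.025 and 0.05/14 = 1/280 = 0.00357, both exact. As a check on the variance formula used below, take the Whitehead sample size for an ordinal outcome, N = 12(z₁₋α/₂ + z₁₋β)² / [(log OR)²(1 − Σp̄³)], where p̄ is the average of the two columns of SAP Table 2. The treatment column sums to 99.88%, so the averages are rescaled to 1. This gives Σp̄³ = 0.1266. With log OR 0.5596, two-sided 5% and 90% power, N = 12 × (1.960 + 1.282)² / (0.3132 × 0.8734) = 461.0, or 462 with equal arms, as stated.

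**Inputs for Phase 2b.** 50 per arm (SAP 2.5) and 1:1:1 allocation (SAP 2.1). OR 1.75 is an assumption carried over from Phase 3.

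**One dose against SOC.** V = (100/12) × 0.8734 = 7.278 and √V = 2.698. The drift is 0.5596 × 2.698 = 1.510. The two-sided critical values are 2.241 (at 0.025) and 1.960 (at 0.05). Power at 0.025 is Φ(1.510 − 2.241) = 23.2%.

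**Two doses.** The two test statistics are taken as bivariate normal with correlation 0.5, because the arms are equal and share the SOC group. Power or rejection rates, Bonferroni → Holm:

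| Scenario, 50 per arm | Stronger (or each) dose | Weaker dose | Both | At least one |
|---|---|---|---|---|
| Both OR 1.75 | 23.2% → 26.1% | same | 10.8% → 16.6% | 35.6% → 35.6% |
| One OR 1.75, other half the log OR | 23.2% → 24.0% | 7.0% → 9.1% | 4.1% → 7.1% | 26.1% → 26.1% |
| One OR 1.75, other null | 23.2% → 23.35% | (null) 2.5% → 3.3% | 0.9% → 1.9% | 24.8% → 24.8% |

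The first row is consistent with itself: 23.2 + 23.2 − 10.8 = 35.6 and 26.1 + 26.1 − 16.6 = 35.6. The both-dose gain of 16.6 − 10.8 = 5.8 points is shared equally between the doses, 2.9 points each.

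With 56 per arm (168/3) and both doses at OR 1.75, the figures are 26.0% → 29.2% per dose, 12.7% → 19.1% for both, and 39.2% for at least one under either rule.

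**Error rates.** With both doses null, the family-wise error is about 4.6% under both rules, since both need a first rejection at 0.025. With one dose null and the other effective, the null dose's false-positive rate is 2.5% under Bonferroni. Under Holm it is 3.3% when the other dose has OR 1.75 and 3.9% at OR 2.5 (a value not in the documents, used only to show the range). It approaches 5.0% for a very large effect.

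**The case against.** The strongest objection is that the plan already deals with the loss. Any dose that Holm would add has p < 0.05, and the SAP already lets such a dose count as potentially promising for the next phase. That flag is wider than Holm, because it does not require the other dose to pass first: with both doses at OR 1.75 its per-dose probability is about 33%, against 26% for Holm. This largely stands, and it is why the practical loss is small. The flag is unadjusted, however. With both doses null, the chance that at least one earns it is about 9.1%, so it does not replace a declaration of significance within the 5% bound.

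Second, Bonferroni keeps each dose at 2.5% whatever the other does, and a sponsor wary of chance findings may prefer that. This stands as a matter of preference. A reader might infer that Holm costs nothing in error rate. Only the 5% bound is unchanged; the actual rate for a null dose rises, as shown above.

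Third, the SAP says it chose the most stringent rule on purpose. That sentence directly follows the 0.05/14 category rule, and the text does not settle whether it also covers the dose comparisons. It neither clearly defends the 0.025 rule nor contradicts it.

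Fourth, Bonferroni has simple matching simultaneous intervals (97.5%) and Holm does not. That is true, but SAP 11.1 reports Wald 95% intervals, so the plan does not use this advantage.

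**Conclusion.** The point holds as an optional improvement. Holm keeps the 5% family-wise bound and never rejects less. If both doses have OR 1.75, it adds about 3 points of power per dose and about 6 points for both doses. If only one dose works, it adds about 0.1 point.

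Two stronger readings are tempting, and the documents support neither. One is that the multiplicity rule is a mistake: the fixed 0.025 is valid, prespecified and consistent between protocol and SAP. The other is that Holm gives more power in every sense: the chance of at least one significant dose is identical whatever the effect size, because Holm's first step is the same test at 0.025.

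The power figures rest on an effect size borrowed from Phase 3, the Table 2 distribution, and a normal approximation without the site and age adjustment. Another form of the variance moves the OR 1.75 figures by at most about half a point. The 5% bound and the zero gain for at least one dose depend on none of these assumptions.

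**What to change.** In SAP 11.1, replace both the 2.5% significance level in the model paragraph and the later sentence requiring p below 0.025 with:

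> The two dose comparisons use Holm's procedure at overall two-sided 5%: the smaller p-value is compared with 0.025 and, if significant, the larger with 0.05.

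Changing only one of the two places would leave SAP 11.1 contradicting itself, because Holm may test the second dose at 0.05. Protocol 10.9.1 and the primary efficacy paragraph of the synopsis carry the same 2.5% level, so align them or record the departure in SAP section 13.

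The cost is a few lines of text, with no new data, model or patients, plus the higher false-positive rate for a null dose beside an effective one. If the sponsor prefers to hold each dose at 2.5%, the present rule can stay.
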